(6) First dose of CFZ533 will be administered intravenously pre- or intra-operatively and must be completed by the time of unclamping or up to 6 hours prior to the time of unclamping. Other study drugs (e.g., Tac, MMF, CS) should be started within 24 hours post-transplantation or according to local practice.

(7) First dose of basiliximab induction should be given within 2 hours prior to transplant surgery, or according to local practice. The second dose should be given on Day 4, or according to local practice.

(8) Local laboratory tests include: hematology, urinalysis, serum chemistries, renal function, and coagulation parameters.

(9) Obtained every 15 mins for 2 hrs after the start of the first CFZ533 IV infusion or time of SC injection.

(10) Negative test result must be available prior to randomization/enrollment.

(11) Blood collections and safety assessments should be taken pre-dose if the sampling falls on a dosing day.

(12) Blood draws for trough concentrations should be performed before the next dose is given. In addition, they should be performed locally as shown and additionally 5±2 days following each clinic visit in which doses are changed.

Corporate Confidential Information

(14) All serious adverse events, serious infections and pregnancies must be reported from informed consent until 3 months after his/her last dose of CFZ533 or 2 months

after EoS visit for patients on SoC treatment.

- (15) Induction therapy (e.g., basiliximab) and pre-transplant immunosuppression (if used) should be recorded on the Concomitant Medications CRF page under the Immunosuppressive category.
- (16) Prophylaxis for CMV, PCP, HBV, BK and oral candida to be considered per protocol [Section 5.5.8](#), and recorded on the Concomitant Medications CRF page if administered.
- (17) All patients are expected to continue in the study to Month 6 or 12 and complete the Month 6 or 12 Completion page, regardless of whether they are on or off study medication. If subjects discontinue study treatment, he/she should continue in the study on SOC per local practice and attend study visits to Month 6 or 12. Any permanent discontinuation of the randomized study regimen should be recorded on the appropriate DAR CRF pages. After discontinuation of study regimen, the immunosuppressive regimen prescribed should be recorded on the Concomitant Medications CRF under the Immunosuppressive category.

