- (18) EOI = End of Infusion (IV) or End of Injection (SC). Blood samples obtained immediately after infusion for IV -administered CFZ533 or immediately after injection for SC-administered CFZ533.
- (19) Timepoint calculated from start of infusion for patients on CFZ533 treatment and from Start of Transplant surgery for TAC treatment

1 Introduction

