3.1.4 Part 2 – Arms 2A-2B

Figure 3-3 Part 2 Design

Approximately 45 patients who meet the inclusion criteria will be randomized in a 2:1 fashion within 24 hours pre-transplant to receive one of the 2 treatment arms (Figure 3-3):

1. **Arm 2A**, n=30: Basiliximab 20 mg (Days 1, 4) + **CFZ533 at 10 mg/kg IV** (17 doses) + MMF 1.0g BID + CS
2. **Arm 2B Control/SoC**, n=15: Basiliximab 20 mg (Days 1, 4) + Tac (4-11 ng/mL) + MMF 1.0 g BID + CS

Induction therapy must be started within 2 hours prior to transplantation, or according to local practice.

The first dose of CFZ533 will be administered IV pre-transplant or intra-operatively. Drug administration will begin after randomization and must be completed by the time of unclamping. Subsequent doses of CFZ533 will be administered IV (Arm 2A), over a period of 12 months.

Other study drugs (apart from Basiliximab) should be started within 24 hours post-transplant. The second dose of basiliximab will be administered on Day 4, or according to local practice.

The day of randomization and transplant will be considered to be study Day 1. Further treatment will be given on study Days 3, 7, 15, 29, 43, 57 and then monthly thereafter until Months 12 (up to approximately Day 337). Subjects will then undergo Study Completion evaluations.

The primary endpoint of Part 2 will be assessed to determine whether the success criteria (safety and tBPAR) have been met

Corporate Confidential Information

Corporate Confidential Information

If notable AEs or safety concerns meeting the *a priori*-defined stopping criteria (see [Section 5.5.10](#)) one of the planned dose levels may be changed or discontinued via amendment.

Subjects will undergo Study Completion evaluations at the end of the trial.

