5.3 Treatment assignment

Randomization/Treatment numbers will be assigned to eligible subjects in Part 2 (see [Section 5.5.1](#) for details) prior to surgery. If provided, the Investigator will enter the randomization/treatment number onto the Electronic Case report Form (eCRF).

Patients in Part 1 will be enrolled sequentially across centers and will keep their screening/subject number throughout the trial. Patients in Part 2 will be randomized 2:1 to Arms 2A:2B.

The randomization/treatment numbers will be generated using the following procedure to ensure that treatment assignment is unbiased and concealed from subjects and Investigator staff, as applicable:

- For Part 1, the Investigator or his/her designee will contact the Sponsor at screening or baseline and confirm the subject fulfills the population criteria.
- For Part 2, IRT will be used. IRT is a validated system that automates the random assignment of treatment arms to randomization numbers in the specified ratio. The Investigator or his/her designee will log into the IRT system at screening or baseline and confirm that the subject fulfills the population criteria. The IRT will assign a randomization number to the patient, which will be used to link the patient to a treatment arm. Detailed instructions on the use of the IRT can be found in the separate IRT manual.

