6.6.4.2 Clinical chemistry

Albumin, alkaline phosphatase, total bilirubin, bicarbonate/CO₂, calcium, cholesterol, chloride, creatinine, CK, gamma-GT, glucose, HbA1c, LDH, inorganic phosphorus, lipase, amylase, magnesium, potassium, total protein, AST, ALT, sodium, triglycerides, BUN and uric acid will be measured. At timepoints on 6h, 24h, 48h and 72h samples have to be taken only for Mg, K, creatinine, Ca and glucose.

If the total bilirubin concentration is increased above 1.5 times the upper limit of normal, direct and indirect reacting bilirubin should be differentiated.

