The following imputation method will be applied at each relevant timepoint for patients with missing eGFR values:

1. Patients that lose their graft before the timepoint in question will be assigned a value of zero for their missing eGFR value.
2. Patients that die or are lost to follow-up with a functioning graft before the timepoint in question will have an imputed value using the last-observation-carried-forward (LOCF) method.

Graft loss patients do not have a functioning graft, hence the lowest possible eGFR value (zero) will be assigned to such patients with missing eGFR values. In contrast, patients that die with a functioning graft, die for different reasons such as suicide, car accidents, cancer, therefore if they have a missing eGFR value, an imputed value using the LOCF method will be used. Similarly, patients who are lost to follow-up and have renal function, but are missing a Month 6 or Month 12 value for various reasons (e.g. moving from the area or not being able to make the site visit during the Month 6 or Month 12 visit) will have an imputed value using LOCF method for any missing eGFR value.

The mean eGFR results will be estimated from a longitudinal repeated measures mixed effects model using all the individual data collected until the timepoint of interest (1st IA Month 3 visit, 2nd IA Month 6 visit) whilst the patient is on treatment. From the model, estimates of the average at the timepoint of interest, treatment difference and 90% confidence

intervals will be obtained. The model will include fixed effects for treatment, time, donor age, donor type (living or deceased) and donor characteristic, treatment by time interaction and donor type by treatment by time interaction. An unstructured variance-covariance structure shall be used, however in the case that the model fails to converge, alternative structures would be tested. The estimates of the adjusted means and two-sided 90% CIs obtained from the model will be plotted over time.

The donor characteristic is a category that could have the result of “standard” or “expanded”.

Vital signs

All vital signs data will be listed by treatment, patient, and visit/time and if ranges are available abnormalities (and relevant orthostatic changes) will be flagged. Summary statistics will be provided by treatment and visit/time.

ECG evaluations

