All ECG data will be listed by treatment, patient and visit/time, abnormalities will be flagged. Summary statistics will be provided by treatment and visit/time.

Clinical laboratory evaluations

All laboratory data will be listed by treatment, patient, and visit/time and if normal ranges are available abnormalities will be flagged. A separate listing is provided presenting all parameters in a patient with any abnormal values. Summary statistics will be provided by treatment and visit/time.

Special clinical laboratory evaluations

Coagulation parameters prothrombin time and partial thromboplastin time will be listed by treatment, patient and visit/time. The coagulation parameters will also be presented graphically to show the overlaid patient profiles and mean profile over time for each parameter separately. Additionally overlaid patient profiles and mean profile over time will be presented graphically for platelets.

Cytokine assessments via multiplex cytokine including TNFa, IFNg, IL1b, IL2, IL4, IL8, IL10, IL12p, IL70 and IL13 will be listed by treatment, patient, and visit/time. The cytokine assessments will also be presented graphically to show the overlaid patient profiles and mean profile over time for each parameter separately.

Donor specific antibodies will be listed by patient and visit.

Immunogenicity data consisting of anti-CFZ533 antibodies information will be listed by patient and visit.

Virology monitoring results for hepatitis B, hepatitis C, HIV, Epstein-Barr Virus (EBV), cytomegalovirus (CMV) and BK virus will be listed by patient, and visit/time and if normal ranges are available, abnormalities will be flagged. The frequency of EBV, CMV and BK virus will also be summarized by treatment.

Adverse events

All information obtained on adverse events will be displayed by treatment and patient.

AEs and infections collected are to be coded with the MedDRA dictionary that gives preferred term and primary system organ class information. AEs and infection preferred terms are to be analyzed as a whole under the heading of AEs. Depending on the number of AEs in Part 2, the incidence of AEs will be summarized by body system, severity and relationship to study drug by the following where possible:

- AEs by primary SOC and PT
- AEs rated to have relationship to study drug by SOC and PT
- AEs by primary SOC, PT, and maximum severity
- SAEs by SOC and PT
- SAEs rated to have relationship to study drug by SOC and PT
- Deaths by SOC and PT

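### In Part 2 the 6, 24, 48 and 72 h timepoints start from a different event in each arm, so early safety chemistry summarised by nominal time compares grafts of different age

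*Protocol*

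**What the plan says.** **Time zero.** Footnote 19 to the protocol's assessment schedules reads: "Timepoint calculated from start of infusion for patients on CFZ533 treatment and from Start of Transplant surgery for TAC treatment". In the visible Part 1 grid it is attached to the 6, 24, 48 and 72 h columns.

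**First infusion.** Protocol 3.1.4 says for Part 2: "The first dose of CFZ533 will be administered IV pre-transplant or intra-operatively". Footnote 6 adds that it "must be completed by the time of unclamping or up to 6 hours prior to the time of unclamping". Protocol 5.5.4 and SAP 1.4.2 give the same window.

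**What is sampled.** Protocol 6.6.4.2: "At timepoints on 6h, 24h, 48h and 72h samples have to be taken only for Mg, K, creatinine, Ca and glucose". The Part 2 blood log (Appendix 1) has local laboratory draws at those four times.

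**Comparison.** Protocol 5.3: "Patients in Part 2 will be randomized 2:1 to Arms 2A:2B", with 30 and 15 patients planned.

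**Analysis.** SAP 7.1.2 on clinical laboratory data: "All laboratory data will be listed by treatment, patient, and visit/time and if normal ranges are available abnormalities will be flagged", and then: "Summary statistics will be provided by treatment and visit/time". Protocol 9.5.3.2 says the same. The SAP eGFR mixed model is fitted "using all the individual data collected until the timepoint of interest" while the patient is on treatment. It includes a treatment-by-time term, and adjusted means are plotted over time.

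No visible text in either document re-anchors the early laboratory samples to unclamping or reperfusion.

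**The concern.** Infusion start is the natural clock for CFZ533 concentrations, receptor occupancy and infusion safety. It is not the natural clock for comparing creatinine, potassium or glucose between arms, because these depend on how long the new graft has been perfused. The protocol itself uses reperfusion as the graft's reference elsewhere: delayed graft function is dated from it (5.5.5), as are the latest start times of MMF and tacrolimus (5.5.4).

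Under footnote 19, patients with the same nominal time in the two arms can have grafts of different age. A CFZ533 patient whose infusion ends 6 h before unclamping reaches nominal 6 h before unclamping, whatever the infusion's length. That sample is a pre-graft value filed under a post-transplant label. With 30 and 15 patients, an early difference in renal chemistry produced by the clock could be read as a drug effect on graft recovery, or could mask one.

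**Working it through.** There is no plan figure to reproduce; the check is timing arithmetic.

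**Does the rule reach Part 2?** The Part 2 grid is redacted. Application there is inferred from three facts. The footnotes are shared by both parts. All Part 1 patients receive CFZ533, so the tacrolimus wording can only serve the Part 2 control arm. The Part 2 blood log has the same four times.

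**Inputs.**
- Gap from end of infusion to unclamping: 0 to 6 h (footnote 6).
- Infusion duration D: not in the documents; assumed 1 h, range 0.5 to 2 h.
- Surgery start to unclamping S: not in the documents; assumed 2 h, range 1 to 4 h.

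**Formulae.** Graft age at nominal time t:
- CFZ533: t − (D + gap)
- Control: t − S
- Difference, CFZ533 minus control: S − D − gap

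**Central case, S = 2, D = 1.** With gap 6 the difference is 2 − 1 − 6 = −5 h. With gap 0 it is 2 − 1 − 0 = +1 h. It is zero at gap = S − D = 1 h.

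| Nominal time | Control graft age | CFZ533 graft age |
|---|---|---|
| 6 h | 4 h | −1 to 5 h |
| 24 h | 22 h | 17 to 23 h |
| 48 h | 46 h | 41 to 47 h |
| 72 h | 70 h | 65 to 71 h |

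A negative age means before reperfusion.

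**Full assumed range.** The extremes are 1 − 2 − 6 = −7 h and 4 − 0.5 − 0 = +3.5 h.

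**What this could do to eGFR, if these records are used.** Illustrative assumptions, none from the documents: creatinine starts at 6 or 8 mg/dL and falls after reperfusion to 1.4 mg/dL, C(t) = 1.4 + (C0 − 1.4) × 0.5^(t/h), with half-time h of 12, 24 or 36 h; C = C0 before reperfusion; non-black man aged 50. The protocol's MDRD formula then gives 186.3 × C^(−1.154) × 50^(−0.203). Control surgery starts 2 h before unclamping. The entries are CFZ533 relative to control with no drug effect.

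| Infusion start before unclamping | 6 h | 24 h | 48 h | 72 h | Largest absolute difference (mL/min/1.73m²) |
|---|---|---|---|---|---|
| 1 h | +1.7 to +5.4% | +1.5 to +3.8% | +1.2 to +1.9% | +0.4 to +1.3% | +0.9, at 24 h |
| 4 h | −3.3 to −10.1% | −3.0 to −7.5% | −2.5 to −3.7% | −0.8 to −2.6% | −1.7, at 24 h |
| 7 h | −6.5 to −19.4% | −7.4 to −18.2% | −6.3 to −9.1% | −2.1 to −6.5% | −4.2, at 24 h |

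The 7 h row is the extreme allowed by footnote 6 when D = 1 h.

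**Late endpoints.** Month 3 is 84 days, or 84 × 24 = 2016 h. A 5 h shift is 5/2016 = 0.25% of elapsed time.

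**The case against.** The strongest reply is that no planned conclusion depends on this. The primary endpoint is tBPAR at Month 3, and the renal comparisons are at Month 3 and later. That stands: only descriptive Day 1 to 4 output is at risk.

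Second, the route into eGFR is not established. SAP 7.1.2 takes eGFR from the central laboratory. Protocol 9.5.3.1 uses local creatinine, and footnote 8 places chemistry and renal function with the local laboratory. The SAP does not say which visits enter the mixed model. This also stands, so the eGFR effect is conditional.

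Third, the size rests on outside assumptions, and the direction is not fixed. The shift can be zero for a given patient, and neither anchor is reperfusion, so graft age varies within each arm too. All of this stands. What survives is that the stated rule gives no common graft age and permits pre-reperfusion samples at nominal 6 h.

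Fourth, the infusion clock has a safety purpose: footnote 9 times early vital signs from infusion start, and protocol 3.6.3 ties close observation to the first hours of exposure. Moving the draws themselves would weaken this, which is a good reason to leave them alone.

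Three stronger readings are tempting and not supported:
- **Setting the early difference against 6.5 mL/min/1.73m².** Protocol 9.7 gives that figure for the key secondary eGFR comparison, which 9.5.3.1 evaluates at Month 12. It is no yardstick for creatinine still falling in the first days.
- **A biased proportion with negative eGFR slope.** No visible text defines the slope or its starting visit.
- **A systematic handicap to CFZ533.** The infusion window allows shifts in either direction.

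**Conclusion.** The point holds as a minor one. Footnote 19, read with the infusion window, means that early Part 2 chemistry summarised by arm and nominal time is compared at graft ages that can differ by several hours in either direction: about −5 to +1 h under S = 2 h and D = 1 h, and −7 to +3.5 h over the wider assumed range. It matters most at 6 h, where some CFZ533 samples may precede reperfusion, and the relative effect is smallest by 72 h.

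If early creatinine does enter the eGFR outputs, the illustrative artefact is at most 1.7 mL/min/1.73m² with infusion 4 h before unclamping, and about 4.2 only in the extreme case. No effect on potassium or glucose was estimated. tBPAR and the Month 3, 6 and 12 eGFR means are essentially unaffected. The conclusion rests on the inference that footnote 19 governs the redacted Part 2 grid.

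**What to change.** Leave the draw times, vital signs and infusion clock for PK/PD and infusion-safety monitoring as they are. Add to SAP 7.1.2, for between-arm summaries of the 6 to 72 h chemistry and of any eGFR derived from it:

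- assign records in both arms to time windows by actual hours since unclamping;
- exclude samples drawn before unclamping from the post-transplant summaries.

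The cost is a short SAP paragraph and some programming, with no extra draws. It needs the unclamping time and the local-laboratory draw times in the database, which the visible text does not confirm. Protocol 6.3 records information on the transplant procedure, and actual collection times are required for PK samples (6.7.1) and centrally analysed samples (5.5.4), but no visible text requires these two items. Check this first. Some early windows may also hold fewer patients.

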1.1 Background

Over the past decades, organ allotransplantation has become a common medical procedure with considerable impact on extending and improving the quality of life of patients with end stage renal, cardiac, hepatic or pulmonary failure. To maximize efficacy and minimize adverse effects, current immunosuppressant (IS) regimens use combinations of IS drugs. Care is taken to achieve synergy or additive immunosuppressive effects via the administration of submaximal doses of individual agents with different mechanism of actions while avoiding overlapping toxicities. Most treatment regimens today include two or more primary and adjunct immunosuppressants with or without an induction agent. Induction agents are administered during the first hours to days post transplantation to suppress the recipient's immune system and priming of an immune response to the allograft while the other IS agents are reaching effective concentrations. Induction agents include the anti-CD25 mAb basiliximab (Simulect®, Novartis) or polyclonal anti-T cell globulin (Thymoglobulin®, rabbit ATG, rATG, Genzyme). In highly sensitized patients, induction with an anti-CD52 mAb, alemtuzumab (Campath®, Sanofi-Aventis SA) which leads to long-term lymphocyte depletion has been used. Within 1-2 days following transplant, the maintenance treatment regimen is initiated with two or more of the following agents: a calcineurin inhibitor (CNI) such as cyclosporine (CsA, Neoral®, Novartis) or tacrolimus (Tac, FK506, Prograf®, Astellas), together with a lymphocyte proliferation inhibitor such as mycophenolic acid (MPA; Myfortic®, Novartis) or mycophenolate mofetil (MMF; CellCept®, Roche) or proliferation signal inhibitor such as everolimus (Zortress®, Certican®, Novartis) or sirolimus (Rapamune®, Pfizer). More recently, the T cell co-stimulation blocker belatacept (Nulojix®, BMS), a fusion protein, demonstrated the potential of a biologic agent to replace CNIs in a calcineurin-free treatment regimen with MPA.

Although the current standard-of-care regimens provide excellent short-term efficacy with very low acute rejection rates, there is still an opportunity to increase long-term graft and patient survival. The current rate of renal allograft graft survival in the first year and 5 years post-transplant is 95% and 68% ([Matas et al 2013](#)), respectively, with a rapid decline thereafter. The estimated glomerular filtration rate at 12 months has been strongly associated with subsequent graft failure ([Kasiske et al 2011](#)). As such, kidney allograft function is also an important predictor of graft survival. Other factors, such as donor age, acute rejection and vascular remodeling may also play a role in overall graft survival, but the nephrotoxic effects of calcineurin inhibitors are directly associated with irreversible renal function deterioration ([Naesens et al 2009](#)). By eliminating CNIs from the treatment regimen, mechanism-based side effects, such as nephrotoxicity, hypertension, dyslipidemia, neurotoxicity, gastrointestinal and hematological toxicity, and/or diabetogenic effects may be minimized or eliminated. In the search for novel therapeutics, there has been an increasing interest in the role B cells, plasma cells and antibodies play in the immune response to an allograft, specifically acute cellular rejection and chronic humoral or antibody mediated rejection ([Clatworthy 2011](#)). By developing a specific treatment that decreases the priming of T and B cells and subsequent production of donor specific antibodies and eliminating CNIs, it is hypothesized that chronic

[figure not shown]
rejection can be minimized and long-term graft survival may be increased. Hence, there is a significant need for new immunosuppressant agents.

1.1.1 CD40/CD40L co-stimulation: a target for transplantation

CD40 is a transmembrane glycoprotein constitutively expressed on B cells and antigen-presenting cells (APCs) such as monocytes, macrophages, and dendritic cells (DC). CD40 is also expressed on platelets, and under specific conditions can be expressed on eosinophils and activated parenchymal cells. Ligation of CD40 on B cells results in downstream signaling leading to enhanced B cell survival and important effector functions, including clonal expansion, cytokine secretion, differentiation, germinal center formation, development of memory B cells, affinity maturation, immunoglobulin (Ig) isotype switching, antibody production and prolongation of antigen presentation. CD154-mediated activation of the antigen-presenting cell (APC) also leads to induction of cytokine secretion and expression of surface activation molecules including CD69, CD54, CD80, and CD86 that are involved in the regulation of CD4+ T helper cell and CD8+ T cell cross-priming and activation.

CD154 exists in two forms – membrane-bound and soluble. Membrane-bound CD154 is a transmembrane glycoprotein expressed on activated CD4+, CD8+, and $\gamma\delta$ T-lymphocytes, mast cells, monocytes, basophils, eosinophils, natural killer (NK) cells, activated platelets and has been reported on B cells. It may also be expressed at low levels on vascular endothelial cells and up-regulated during local inflammation. Soluble CD154 (sCD154) is formed after proteolysis of membrane-bound CD154 and is shed from lymphocytes and platelets following cell activation. Once shed, sCD154 remains functional and retains its ability to bind to the CD40 receptor.

Figure 1-1 Roles of CD40-CD154 signaling in the T and B cell

Targeting CD40-154 interactions in transplantation and autoimmune disease. CD40-CD154 interactions are essential for APC activation, T cell priming in the context of APC-T cell interactions and T cell dependent humoral responses.

NOTE: mCD154=membrane bound CD154; sCD154=soluble CD154

The critical role of CD40/CD154 interactions *in vivo* are best illustrated by patients suffering from Hyper-Immunoglobulin M (HIGM) as a result of loss of function mutations in CD40 or its ligand. Patients with HIGM present with a severe impairment of T cell dependent antibody responses, lack of B cell memory, and little to no circulating IgG, IgA or IgE. In patients with mutations in CD40 signaling, a similar phenotype and disease presentation has been described (van Kooten and Banchereau 2000).

Corporate Confidential Information

Using monoclonal antibodies to target CD154 has been hampered by the occurrence of thromboembolic complications (Kawai et al 2000) so an alternative approach is to target the receptor, CD40.

